5.0 Inclusion and Exclusion Criteria/ Study Population

Twenty participants with upper extremity post-stroke pain of all ethnic and racial categories will be accepted into this study protocol. No preference will be given based on race, gender, or ethnicity. Pregnant females and children under the age of 18 will be excluded for safety reasons.

Inclusion Criteria:

- Age 18-80
- Have the capacity and ability to provide one’s own consent in English and sign the informed consent document.
- Ischemic or hemorrhagic stroke that occurred at least 6 months prior
- Unilateral stroke lesions in the left hemisphere
- Right upper extremity pain

Exclusion Criteria:

- Primary intracerebral hematoma or subarachnoid hemorrhage
- Documented history of dementia

- Documented history of uncontrolled depression or psychiatric disorder
- Uncontrolled hypertension despite treatment, specifically SBP (Systolic Blood Pressure) / DBP (Diastolic Blood Pressure) $\geq 180/100$ mmHg
- Pregnancy

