channels of stimulation (auricular vagus, auricular trigeminal, and both). Two individual stimulation frequencies will be set: 15 Hz at cymba concha and 100 Hz adjacently anterior to tragus. The pulse duration will be set to 250 μ s for all participants. The stimulation intensities delivered (in mA) will be a standardized 2X Perceptual Threshold. This means that all individuals will first have a perceptual threshold conducted, during which incremental increases and decreases in current intensity will be applied until the participant barely feels the stimulation. That is considered the perceptual threshold. All stimulation then will be delivered at 2X this value. Perceptual threshold will be conducted at the beginning of the taVNS intervention. This is how we have conducted stimulation at MUSC in prior IRB-approved studies which have been safe and rated comfortable and not painful. Sham stimulation will be administered at identical parameters of cymba concha, however, the electrodes will be attached to the earlobe, which is not believed to have a high density of cranial nerve innervation. If the participant states that the stimulation intensity is discomforting or imperceivable in any of the stimulation groups, the researcher will gradually decrease until a comfortable stimulation intensity is achieved. The taVNS session will last for 30 minutes.

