14.0 Withdrawal of Subjects

Participants will be informed during consenting that they are free to withdraw from the study at any time. They will be informed that they are not obligated to participate once the study is initiated and in particular will be reminded prior to taVNS/VNS stimulation they may discontinue stimulation and/or the experiment at any point. taVNS has been a very safe procedure and we do not anticipate subject withdrawal due to taVNS side effects. No participants in previous studies utilizing taVNS have been forced to withdraw for medical or physiological purposes, and we do not anticipate any issues during this study. If participants begin to experience ear pain, an attempt can be made on the other ear, as well as a reduction in the intensity of stimulation before termination would be required. We will be monitoring the stimulation session and if a patient is extremely sensitive to the device we might consider terminating. In that case, the participant and their guardian would be informed of the need for termination.

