15.0 Risks to Subjects

Ear Stimulation:

Ear stimulation is safe, however, there are some risks associated with stimulating the ear: There may be local discomfort. This will likely be temporary. In extreme cases, burns might occur. We will monitor any potential burns via direct communication with participants and will stop stimulation and advise subjects to apply vitamin E cream. The tissue surrounding the ear may be sensitive, sore, or feel slight numbness. Hopefully, this will be temporary and will go away after the stimulation is turned off.

Safety in Case of Pregnancy:

This protocol will exclude pregnant women. The risks of using taVNS with pregnant women are currently unknown. If in the screening and consent a patient is a woman of childbearing age, they will be tested prior to receiving any taVNS.

Potential Headache, Dizziness, and Facial Pain:

Ear stimulation might cause headaches or face pain, which should resolve shortly after treatment.

Potential Decrease in Heart Rate:

Ear stimulation may slow heart rate. In rare cases (less than 1%) decreased blood pressure or fainting may occur. We expect no significant changes in heart rate or blood pressure, or fainting to occur. For the initial sessions, all subjects will be stimulated while they are seated, never standing. We expect no significant changes in heart rate or blood pressure, but if this occurs, the study team will evaluate the situation and either decide that the patient should be dropped from the study, or do all sessions lying on a couch, or with lower doses.

QST Pain Assessments:

The Medoc pain assessment system has been used safely by Co-I [name] and others for over a decade now. The pain is unpleasant but there are limits to the amount of pain, and there have been no adverse events over 5 prior MUSC IRB-approved pain studies using this approach. Some participants may report feeling anxious before experiencing a painful stimulus, however, this is rare and if occurs, the participant will be able to request to stop voluntarily.

Unknown Risks:

There is always the possibility of other risks for a relatively new technology. The Study team will let the participant know if they learn anything that might make the participant change their mind about participating in the study.

Loss of Confidentiality:

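### The protocol names slowed heart rate, low blood pressure and fainting as stimulation risks but excludes only high blood pressure, so a known history in the low direction excludes no one

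*Protocol*

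**What the plan says.** Section 15.0, under the heading on decreased heart rate, states: "Ear stimulation may slow heart rate. In rare cases (less than 1%) decreased blood pressure or fainting may occur". It adds that no significant change is expected, that participants are stimulated seated, and that if a change does occur "the study team will evaluate the situation and either decide that the patient should be dropped from the study" or continue lying down or at a lower dose.

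Section 5.0 lists five exclusions: primary intracerebral hematoma or subarachnoid hemorrhage; dementia; uncontrolled depression or psychiatric disorder; "Uncontrolled hypertension despite treatment", defined as 180/100 mmHg or above; and pregnancy. The age range is 18 to 80.

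Other provisions bear on the same risk:

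- Section 10.0 sets the dose individually: "The stimulation intensities delivered (in mA) will be a standardized 2X Perceptual Threshold". It is lowered if the participant finds it uncomfortable.
- Section 14.0 reminds participants before stimulation that "they may discontinue stimulation and/or the experiment at any point", and adds: "We will be monitoring the stimulation session and if a patient is extremely sensitive to the device we might consider terminating".

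On pregnancy, Section 5.0 says: "Pregnant females and children under the age of 18 will be excluded for safety reasons". Section 15.0 gives the reason: "This protocol will exclude pregnant women. The risks of using taVNS with pregnant women are currently unknown".

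**The concern.** The stimulation risk that the protocol describes lies in one direction (slow heart rate, low pressure, fainting), while its single blood-pressure exclusion lies in the other. Staff who apply Section 5.0 as written have no criterion for turning away someone known to have symptomatic bradycardia, conduction disease, symptomatic hypotension or recurrent syncope.

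Safety is part of the primary outcome (Section 4.0). An avoidable event in such a participant would be a harm to that person. In a pilot of 20, it would also weigh heavily on the safety result. Eligibility belongs in the protocol, so a statistical analysis plan that is not shown here would not be expected to supply the criterion.

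**Working it through.** The protocol states no figure on this point that could be reproduced. The check sets the eligibility list against the named risks and then puts a bound on scale.

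**1. Exclusions against risks (Section 5.0 against Section 15.0)**

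| Exclusion | Heart rate or blood pressure? | Covers the low direction? |
|---|---|---|
| Primary intracerebral hematoma or subarachnoid hemorrhage | No | No |
| Dementia | No | No |
| Uncontrolled depression or psychiatric disorder | No | No |
| Uncontrolled hypertension, 180/100 mmHg or above | Yes, upper limit | No |
| Pregnancy | No | No |

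Of five exclusions, one concerns heart rate or blood pressure and none covers the low direction. No inclusion criterion does so either.

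**2. Do the other safeguards fill the gap?**

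- Seated posture (Section 15.0) applies to everyone, whatever their history.
- Dosing at twice perceptual threshold (Section 10.0) is individual, but it is set by sensation at the ear. It is reduced for discomfort, not for cardiovascular history.
- Session monitoring (Section 14.0) is described in terms of ear pain and sensitivity to the device. The procedures in Section 10.0 describe no heart-rate or blood-pressure measurement during stimulation.
- Dropping the participant, lying down or reducing the dose (Section 15.0) begins only once a change has occurred. With one visit and one 30-minute session, it cannot prevent that first event.

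The protective measures are therefore either general or reactive. Screening on history is the step that would act before exposure, and it is absent.

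**3. Scale of the general risk**

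Inputs: n = 20 (Section 6.0) and p below 0.01 for decreased blood pressure or fainting (Section 15.0), read as a per-participant rate. No rate is given for slowed heart rate.

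Expected events: n × p = 20 × 0.01 = 0.2, so fewer than 0.2.

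Chance of at least one event: 1 − (1 − p)^n. The row for n = 10 counts active participants only and assumes 1:1 allocation, because the protocol gives no ratio.

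| n | p = 0.001 | p = 0.005 | p = 0.01 |
|---|---|---|---|
| 20 | 2.0% | 9.5% | 18.2% |
| 10 | 1.0% | 4.9% | 9.6% |

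For example, 1 − 0.99^20 = 0.182. The right-hand column is a ceiling, because the stated rate is below 1%.

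These figures describe participants in general. The protocol gives neither the prevalence of the histories in question nor an event rate among people who have them, so the number of events that an exclusion would avert cannot be derived.

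**The case against.** The strongest case against is that nothing in the protocol is wrong or contradictory. A rare risk may be named and then managed by procedure instead of exclusion, and Section 15.0 does that. The step that makes the omission matter, that such a history raises the risk from one ear stimulation, appears nowhere in the protocol. The reported experience is also reassuring: Section 1.0 describes good tolerability in earlier work in chronic stroke, Section 14.0 reports no forced medical withdrawals in previous studies of the technique, and Sections 3.0 and 18.0 class the device as non-significant risk. The pregnancy exclusion is a weak parallel, because it answers an unknown risk, whereas here a ceiling is given. Finally, candidates are further screened (Section 8.0) and phone screened (Section 10.0), and those questions are not shown.

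Much of this stands, and it limits severity. Sections 5.0 and 15.0 are compatible, the absolute risk is small, and the link to history is a clinical assumption. It is, however, an ordinary one when the named effects of the stimulus are slow heart rate, low pressure and fainting. The reassuring experience and the device class do not address people with these histories. The pregnancy exclusion shows only that the protocol will exclude as a precaution without a quantified rate. The unseen screening questions might cover cardiac history, but Section 5.0 would give staff no criterion to act on the answer.

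**Conclusion.** The concern holds as a cheap improvement of low severity. On the text it is certain: Section 5.0 contains no exclusion in the direction of the risk that Section 15.0 names, and no other section supplies one. Its practical importance is less certain. It rests on the assumption that symptomatic bradycardia, conduction disease, symptomatic hypotension or recurrent syncope makes a person more vulnerable to that risk. The absolute gain is probably small, given a stated rate below 1% and a single monitored, seated session, and it cannot be estimated from the protocol. The case for acting is that the safeguard costs very little and safety is part of the primary outcome.

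**What to change.** Add one exclusion to Section 5.0: *Known symptomatic bradycardia or cardiac conduction disease, symptomatic hypotension, or recurrent syncope.* Ascertain it by history with one question at the phone screen already described in Section 10.0. No numeric limit and no new procedure are needed.

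The cost is one line, one question and a short amendment. The downside is a slightly smaller pool from which to recruit 20 participants, and a safety result that applies to a slightly narrower population; the report should say so.

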6.0 Number of Subjects

We will recruit 20 participants with chronic post-stroke upper extremity pain for this study.

7.0 Setting

All participants will complete the study tasks in our experimental room at the MUSC [name] Center for Biomedical Imaging. Subjects will be consented and educated about the study, and complete the rest of the study procedures.

8.0 Recruitment Methods

This study will recruit from the Registry for Stroke Recovery (RESTORE-Pro#00037803, IRB approved 9/6/14) which is a research tool sponsored by the National Institutes of Health (NIH) Center of Biomedical Research Excellence (COBRE) in Stroke Recovery with subjects consented for future contact to support stroke recovery research conducted at MUSC. RESTORE staff will query the registry for potential subjects and provide the Principal Investigator (PI) with the contact information of subjects who meet their criteria. The PI or research staff will then contact subjects to confirm whether they are interested in the study following the cold call recruitment script. Additionally, RESTORE staff can also give rack cards to interested RESTORE (stroke registry) individuals. They will be further screened for potential enrollment.

[figure not shown]
9.0 Consent Process

Consent procedures will be conducted in a private, quiet room at the MUSC [name] Center for Biomedical Imaging. Approved study personnel will walk through the consent procedures with the participants. Furthermore, after the consenting procedures, the consent form will be printed and provided to all participants to independently review to ensure understanding, including describing the laboratory measures, study duration, and equipment and materials. The study team will describe confidentiality/privacy measures, participant right to withdraw, risks/benefits. In addition, participants will be prompted to ask questions throughout consenting to further ensure understanding. After signing the consent form, they will also be offered a hard copy.

10.0 Study Design / Methods

Study Overview:

After determining eligibility and interest, written informed consent will be obtained from participants at the MUSC Center for Biomedical Imaging. After consent is obtained, the participants will then complete a pregnancy test and conduct a brief daily life functioning battery. Enrolled participants will start the experiment. They will first finish the subjective pain rating and have quantitative sensory testing (QST) conducted to determine baseline pain thresholds. Participants will then receive 30 minutes of tVNS (either active or sham). Upon the completion of the stimulation intervention, they will then be tested for another subjective pain rating and QST. The timeline of the experiment and group assignment overview are displayed below.

Experiment Overview – Investigate the anti-pain effect of taVNS in chronic post-stroke upper extremity pain

Recruitment, Screening, and Consent Procedures:

Recruitment will be conducted by the study team utilizing the MUSC RESTORE list to identify and contact prospective chronic stroke patients. Participants who are found to be appropriate candidates will be offered to be phone screened and educated regarding the study's details. If interested in participating in the study, they will be consented and enrolled into the study's protocol. Additionally, RESTORE staff can also give rack cards to interested RESTORE (stroke registry) individuals. If interested in participating in the study, they will be consented and enrolled into the study's protocol.

Daily Life Function Battery:

All participants will complete a daily life function battery after being enrolled. This battery includes the following questionnaires in specific life domains that will be used to identify baseline characteristics of individuals: Demographics; Pain Screening; Substance Use: TAPS; Pain Intensity & Interference: PEG; Physical Functioning/QDL: PROMIS Physical Functioning 6b; Sleep: PROMIS Sleep Disturbance 6a; Sleep: Sleep Duration; Depression: PHQ9; Anxiety: GAD7.

Pregnancy Test Procedures:

If participants are a person of childbearing age, they will be provided with a pregnancy test strip. After completing the pregnancy test, participants with negative results will be asked to continue to the remaining study procedures, whereas those with a positive result will be debriefed and released.

Subjective Pain Rating:

Participants will rate their post-stroke upper extremity pain intensity before and after the taVNS using a standard numeric pain rating scale (0-10).

Quantitative Sensory Testing Procedures:

We will measure pain assessments by administering cutaneous stimuli via the Medoc Pathway System (Medoc, Durham, NC) using a 30 x 30 mm ATS thermode. QST will be done using method of limits testing on the thenar eminence of the non-affective forearm (left arm). A program will be set up to administer 5 hot stimuli with random durations between each trial. The ATS thermode begins at 32 deg C and increases by 0.5 deg C per second. Participants will be asked to press a button in order to signify three different measures: (1) sensory threshold, or the temperature at which the stimulus becomes noticeable, (2) pain threshold, or the temperature at which the stimulus becomes painful, and (3) pain tolerance, or the temperature at which the stimulus becomes too painful to tolerate. Measuring these thresholds will yield information about A β , A δ , and C fibers, respectively. The device will be set to stop heating at 51.5° C and stop cooling at 0° C to avoid tissue damage. The QST procedures will be tested before and after the taVNS.

taVNS Procedures:

All stimulation will be conducted using the Sparrow Ascent transcutaneous auricular neuromodulation (tAN) device manufactured by Spark Biomedical (Dallas, TX). These tAN devices are portable, wearable systems that have 2

channels of stimulation (auricular vagus, auricular trigeminal, and both). Two individual stimulation frequencies will be set: 15 Hz at cymba concha and 100 Hz adjacently anterior to tragus. The pulse duration will be set to 250 μ s for all participants. The stimulation intensities delivered (in mA) will be a standardized 2X Perceptual Threshold. This means that all individuals will first have a perceptual threshold conducted, during which incremental increases and decreases in current intensity will be applied until the participant barely feels the stimulation. That is considered the perceptual threshold. All stimulation then will be delivered at 2X this value. Perceptual threshold will be conducted at the beginning of the taVNS intervention. This is how we have conducted stimulation at MUSC in prior IRB-approved studies which have been safe and rated comfortable and not painful. Sham stimulation will be administered at identical parameters of cymba concha, however, the electrodes will be attached to the earlobe, which is not believed to have a high density of cranial nerve innervation. If the participant states that the stimulation intensity is discomforting or imperceivable in any of the stimulation groups, the researcher will gradually decrease until a comfortable stimulation intensity is achieved. The taVNS session will last for 30 minutes.

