1.0 Objectives / Specific Aims

In this study, our main goal is to establish transcutaneous auricular vagus nerve stimulation (taVNS) as an effective non-invasive neuromodulation method for analgesia of post-stroke upper extremity pain.

We will recruit up to 20 participants with chronic post-stroke upper extremity pain from the greater Charleston area using MUSC COBRE resources. Participants are required to have an ischemic or hemorrhagic stroke that occurred at least 6 months prior and are currently suffering upper extremity pain. Each participant will undergo an in-person visit to our lab at MUSC [name]. They will first finish the pain questionnaires and have quantitative sensory testing (QST) conducted to determine baseline pain thresholds. Participants will then receive 30 minutes of taVNS (either active or sham). Upon the completion of the stimulation intervention, they will then be tested for another QST and pain questionnaires. All research is being done at MUSC [name] Center for Biomedical Imaging.

Aim 1: Test the safety and feasibility of taVNS in participants with chronic post-stroke upper extremity pain.

Over the last 8 years, our group has demonstrated that taVNS is safe and feasible in several different populations in our previous studies. Specifically, we have demonstrated that taVNS is well tolerated and safe for participants with chronic stroke in our previous clinical trial ([name] et al., 2023, [name] et al., 2023). In this study, we will further verify the safety and feasibility of taVNS in the population with chronic post-stroke upper extremity pain.

Aim 2: Investigate whether taVNS can modulate pain in this population compared to sham.

In this single-visit, single-blinded, sham-controlled pilot trial, we will compare changes in post-stroke upper extremity pain scores and pain threshold derived from QST before and after a 30-minute taVNS intervention, as well as between active and sham taVNS. The findings will help us understand whether taVNS can modulate pain in this population.

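### For a stimulus the participant cannot feel, the intensity rule tells the researcher to lower the current, which is the wrong direction (minor, probably a drafting slip)

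*Protocol*

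**What the plan says.** The dosing text is in Section 10.0, under taVNS Procedures. The threshold is found by stepping the current up and down until the participant barely feels it. On timing, the Protocol says "Perceptual threshold will be conducted at the beginning of the taVNS intervention". On dose, it says "All stimulation then will be delivered at 2X this value".

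One adjustment rule follows, and it covers both arms. If the participant reports the intensity as "discomforting or imperceivable in any of the stimulation groups, the researcher will gradually decrease until a comfortable stimulation intensity is achieved".

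Two other places allow the intensity to change after the threshold is set:

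- Section 14.0: "If participants begin to experience ear pain, an attempt can be made on the other ear, as well as a reduction in the intensity".
- Section 15.0, for changes in heart rate or blood pressure: the team will "either decide that the patient should be dropped from the study, or do all sessions lying on a couch, or with lower doses".

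Section 1.0 (Aim 2) describes a "single-visit, single-blinded, sham-controlled pilot trial" with one 30-minute stimulation period.

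**The concern.** The rule ties two opposite complaints, too strong and not felt, to a single action. That action suits only the first. Naming an unfelt stimulus as a reason to intervene makes sense only if the intervention is meant to make it felt, and a decrease cannot do that.

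This is an instruction that staff carry out during the session, not an analysis detail that an SAP would settle. Section 12.0 says that personnel are trained in the protocol and that data collection is monitored for adherence to it. A researcher who sensibly raises the current therefore departs from the written rule. One who follows the rule either does nothing or lowers the dose. Different operators could resolve it differently, although the dose is described as standardized. Each participant has one session, so a session handled wrongly is not repeated.

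**Working it through.** The Protocol gives no figure to reproduce here. The check is a reading of the rule with simple notation, followed by a search for a correction elsewhere.

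**Inputs.** Let T0 be the perceptual threshold measured at the start (Section 10.0). The assigned current is I = 2 × T0 (Section 10.0). The triggers are discomfort or absence of sensation, the action is a decrease, and the stopping condition is a comfortable intensity (Section 10.0). No step size, floor or maximum current is stated.

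**Discomfort branch.** The current is lowered until comfortable. Trigger, action and stopping condition agree. There is no problem here.

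**Unfelt branch.** There are two literal readings.

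- *Reading A.* An unfelt stimulus causes no discomfort, so the stopping condition is already met. No step is taken, the current stays at 2 × T0, and the stimulus stays unfelt. The trigger has no effect.
- *Reading B.* The researcher takes at least one step down by a fraction d > 0. The current becomes 2 × T0 × (1 − d), which is below 2 × T0. Because d and a floor are not given, the only supported bound is less than 2X. The stopping condition refers to comfort and not to perception, so it cannot show that the problem has been solved.

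Neither reading restores a perceptible stimulus.

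**How unusual the trigger is.** With the electrodes in contact, a current of 2 × T0 is unfelt only if the present threshold T1 exceeds 2 × T0. Either the threshold has more than doubled since it was measured, or T0 was recorded too low. The remaining explanation is lost contact. The Protocol gives no frequency for any of these.

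**Search for a correction.** Upward steps appear in Section 10.0 only as part of finding the threshold. Section 14.0 (ear pain) and Section 15.0 (heart rate or blood pressure) provide reductions. That is proper for those triggers, but it leaves the unfelt branch uncorrected. No section calls for the threshold to be checked again.

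**What limits an upward step.** Section 15.0 warns "In extreme cases, burns might occur" and "Ear stimulation may slow heart rate". A participant who cannot feel the stimulus may not report discomfort in time, so an increase needs a ceiling. Setting a new target of twice the present threshold would be a large change: since T1 > 2 × T0, it would mean 2 × T1 > 4 × T0. A cautious increase to a perceptible, comfortable level is the smaller departure.

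**The case against.** The strongest reply is that this is a slip for a neutral verb such as adjust. The threshold step in the same paragraph already uses both increases and decreases, and a researcher told that nothing is felt is unlikely to turn the current down. The event is also remote at twice a current just reported as felt. Lost contact would be dealt with by reseating the electrode in a session that Section 14.0 says is monitored, and a wrongly set threshold is a failure of the threshold step itself. Fading sensation is then the main remaining cause, and that it occurs is an assumption. All of this stands, and it is why the point is minor. It does not make the text right. The intended upward procedure cannot be recovered from the Protocol, and replacing one word would permit an increase with no ceiling.

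A reader might go further and infer that the rule under-doses participants and so weakens the active-versus-sham comparison in Aim 2. The documents do not support that. Dose is defined by the threshold measured at the start, so under Reading A the participant receives exactly the assigned 2X. The Protocol nowhere says that the effect on pain depends on continued sensation. Only Reading B lowers the dose, and neither its frequency nor any resulting loss of effect can be derived. Nor does it measure impact that the two other intensity rules also only reduce, or that one participant is 1/20 = 5% of the sample. The first shows only that nothing elsewhere corrects the branch. The second is the weight of any participant.

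**Conclusion.** The rule is wrong as written for an unfelt stimulus, and nothing else in the Protocol corrects it. That conclusion rests on the text alone. Severity is minor. In the literal case the current either stays at 2X the initial threshold or falls below 2X by an amount that cannot be stated. The case should be rare, and no effect on safety and feasibility (the primary outcome in Section 4.0) or on the Aim 2 comparison has been shown. The judgement that it is rare rests on the dose being twice a just-felt current, since no frequency is given.

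**What to change.** Split the sentence in Section 10.0 into two rules for both arms:

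- If the stimulation is uncomfortable, lower the current gradually to a comfortable level.
- If it is not felt, do not lower it. Check electrode contact and the initial threshold setting. If it is still not felt, raise the current gradually until it is perceptible and comfortable, without exceeding a maximum current (mA) stated in the Protocol.

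The sponsor must supply the maximum, since the document gives none. Record the final delivered mA for every participant.

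The cost is one or two sentences, one data field and a short interruption in the rare affected session. Sample size, visits and endpoints do not change. The small downside is that a few participants may receive a multiple other than 2X of their initial threshold, which the recorded mA would show. Requiring a new threshold and a fresh 2X target during the session is not needed, and it would replace the fixed dose reference.
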